(excluding anorexia nervosa, for which more intensive medical monitoring is warranted), which account for a substantial proportion of the mental health burden on college campuses, and who are not currently engaged in mental health services (N=7,884; of 146,000 initially screened) will be randomly assigned to: 1) intervention via the mobile mental health platform; or 2) referral to usual care (i.e., campus health or counseling center). Our comprehensive mental health care platform can yield clinical benefit to students, appeal to university stakeholders, minimize barriers to implementation sustainability on campuses, and produce an economic return on investment compared to usual care. This population-level approach to service engagement has the potential to improve mental health outcomes for the 20+ million students enrolled in U.S. colleges and universities.

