Following the personalized feedback, students meeting study eligibility criteria will receive a brief statement of eligibility for and description of the study purpose and duration, activities involved, and assessment time points. Students will be asked to confirm their willingness to continue. If they agree students will be asked for their email address and phone numbers, and will be provided a link to the Phase 2 survey. After giving online consent, participants will be randomized via a code through Qualtrics into one of two conditions:

- 1) Intervention: receiving access to our mobile coached self-help program for 6 months.
- 2) Control: Receiving information on how to receive treatment at the student's counseling center on campus.

Participants will then complete the baseline survey, which will assess treatment expectancy/credibility, cognitive distortion, impairment/quality of life, motivation for treatment, and mental health treatment utilization. After completing these measures students will be made aware of the condition they were randomized into and asked to complete a short Treatment Credibility and Expectancy Questionnaire.

Individuals who choose not to continue will receive their screen feedback through Qualtrics, a recommendation to seek care, and a campus-specific list of resources.

After completing the baseline survey participants will receive an email and text message with information about their screen responses and either a link to the mobile intervention or information on how to access clinical services, based on their randomized condition. Individuals who screen positive or at high risk for more than one of the three mental health disorders (anxiety, depression, EDs) will be asked to select which problem is most bothersome or impairing to their everyday functioning, which has been shown to correlate with provider ratings, and will then be directed to focus primarily on that problem using either the mobile app or in-person services.

---

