All students in the usual care condition will receive a recommendation to seek care and will be given a list of resources available through their respective health or counseling center, including contact information to make an appointment and any other relevant resources on campus. Participants who will be completing the mobile interventions will be given a link to the program, hosted on a platform by our technology partners SilverCloud Health, and a program description. They will also be provided with instructions to download the SilverCloud Health program app, through which they can access the intervention, as well. Students are encouraged to log in to the intervention, create an anonymous username and password, and begin the program.

Both intervention and control groups will be asked to complete assessments at 6 weeks, 6 months, and 2 years after completing the baseline screen. 6 week assessments will ask participants to complete assessments of anxiety, depression, EDs, motivation for treatment, and mental health treatment utilization. The 6 month and 2-year follow-ups will include assessments of anxiety, depression, EDs, comorbidities, impairment/quality of life, motivation for treatment, mental health treatment utilization, and screening and treatment feedback. In addition, alternate contact information will be requested at baseline, 6, and 12 month follow-ups in order to maximize the likelihood that participants can be reached at the next follow-up assessment, including cell phone number for receiving SMS text-message reminders for follow-up surveys to be sent from the Qualtrics platform. Follow-up emails and SMS may also use images or other media to increase the students' attention and likelihood of response. In order to increase the response rate at 2-year follow-up the study team may call participants to remind them to complete the survey, the study team may leave a voicemail if the participant does not respond. All assessments will be conducted using Qualtrics survey platform.

Participants will be compensated by receiving an electronic gift card for completing the Baseline (\$5), 6 week (\$5), 6 month (\$10), and 2-year (\$20) follow-up assessments. Participants will be entered into a sweepstakes to win one of five \$50 gift cards after completing the Baseline, 6 week, 6 month, and 2-year surveys. In addition, once participants complete all four surveys, they will be entered into a sweepstakes to win one of ten \$100 gift cards.

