In the case of imminent risk, such as in the extremely rare case of a user reporting plans of suicide or homicide, there are several steps that coaches for students engaging in the mobile program are mandated to take as mandated reporters. First, coaches contact a coach supervisor and the Fidelity Monitoring Center either by phone or an email marked URGENT to consult about how to proceed as soon as possible. If coaches do not receive a response within an hour, they will reach out to a back-up coach supervisor. Second, coaches identify the appropriate local agency such as the campus police at the user's college or university to prepare for possibly making a report. Next, they provide the user with a variety of emergency options such as counseling center information, suicide hotline phone number, emergency room location, or local police information and encourage clients to seek additional support or hospitalization through these options. Coaches also gather relevant information by reviewing the coaching record for all identifying information available such as name, age, phone number, and email address to provide to the agency when making a report. If it is deemed appropriate by the coaching supervisor, coaches call in the report as soon as possible to the identified local agency. They also follow up with the user, express concern, provide support, and let him/her know a report has been made. In addition, coaches follow up with the coach supervisor and the Fidelity Monitoring Center via email to let him/her know the report was made. Finally, coaches continue to monitor the user for emerging or worsening risks, as demonstrated by information the user inputs into the program or messages to the coach, and they continue to keep in close contact with the coaching supervisor. Should the user continue to worsen and be deemed at continued imminent risk, the coach and coach supervisor may make a decision to withdraw the participant from the program.

In the case that individuals endorse criteria for possible AN (low weight and significant weight shape concerns) at the 6-month or 2-year follow-up assessments, they will be offered a referral for in-person treatment.

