Participants completing the mobile intervention will receive the support from a coach. Their role includes supporting and enhancing user motivation; monitoring progress; facilitating goal setting and offering accountability; providing feedback on technique usage and encouraging practice; answering user questions; and monitoring for/responding to clinical risk. Communication with users is primarily via two-way, asynchronous messaging, with optional, supplementary phone calls to enhance goal setting. Coach messaging is done via a web-based "dashboard," and delivered to users within the SilverCloud Health app. Coaches have participants' baseline screen results so they can personalize treatment and help the user apply skills learned to comorbid problems. Moreover, coaches will monitor symptoms using the following assessments built into the SilverCloud Health programs:

- 1) For individuals with depression, depression is assessed weekly using an abbreviated version of the measure used for assessing depression at baseline (i.e., PHQ-2).
- 2) For individuals with anxiety, anxiety is assessed weekly using a short, validated measure of anxiety (i.e., GAD-2).
- 3) For individuals with eating disorders, weekly monitoring includes three questions based on the EDE-Q assessing eating disorder behaviors (i.e., binge eating, purging) and weight/shape concerns.

Note: When individuals have more than one of these problems, they complete weekly monitoring for each comorbidity.

If the coach feels the online program cannot adequately address comorbidity, participants are referred to appropriate campus/community resources.

The program will be accessible via smart phone app or their desktop. Program access will be password protected.

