### ***E2 Schedule of Measurements***

Participants will be assessed at screening, baseline, 6 weeks, 6 months, and 2 years. All surveys will be administered via Qualtrics. Participants will be compensated by receiving an electronic gift card for completing the Baseline (\$5), 6 week (\$5), 6 month (\$10), and 2-year (\$20) follow-up assessments. Participants will be entered into a sweepstakes to win one of five \$50 gift cards after completing the Baseline, 6 week, 6 month, and 2-year surveys. In addition, once participants complete all four surveys, they will be entered into a sweepstakes to win one of ten \$100 gift cards.

---

All students who receive a recruitment email will be automatically entered into a sweepstakes for one of 40 \$100 electronic gift card prizes.

See table below for schedule of assessments:

	Baseline Screen	Intervention Period	Post-Screen Assessments			Primary Purpose
			6 wks	6 mos	2 yrs	
PARTICIPANTS						
Demographics	x					Mod
Expectancy/credibility	x					Mod
Degree of cognitive distortion	x					Mod
Anxiety: Generalized anxiety; social phobia; panic	x		x	x	x	TO/Mod (symptom severity; comorbidity)
Depression	x		x	x	x	TO/Mod (symptom severity; comorbidity)
Eating disorders	x		x	x	x	TO/Mod (symptom severity; comorbidity)
Chronicity	x					Mod
Comorbidities: Trauma; insomnia; substance use	x			x	x	Mod
Impairment/quality of life	x			x	x	TO/Mod
Motivation for treatment	x		x	x	x	Mod
Mental health treatment utilization	x		x	x	x	TO
Academic impairment (obtained from colleges)	x			x	x	TO
Target engagement Transdiagnostic : dysfunctional cognitions; CBT skills Disorder-specific : avoidance; behavioral activation; restraint; weight/shape concerns	x		x			Med
Early engagement			x			Med
Rapid response			x			Med
Screening and treatment feedback				x	x	--
TREATMENT PROCESS (INTERVENTION CONDITION)						
Mobile treatment process (e.g., sessions completed, messages with coach)		x				Pred
Fidelity/personalization of coaching (i.e., user perception and coder ratings)		x	x	x		Pred
STUDENT MENTAL HEALTH SERVICES CENTERS						
Attitudes toward mobile mental health platform	x					--
Perceptions of mobile mental health platform				x		--
Intended adoption					x	--
Mental health service utilization	x				x	TO

Notes: Light gray shading = occurring during intervention period. Mod = moderator; TO = treatment outcome; Med = mediator; Pred = predictor.

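### Minor safety improvement: the referral for possible anorexia nervosa starts at 6 months, though eating disorders are already assessed in both arms at 6 weeks

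*Combined protocol and SAP*

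**What the plan says.** The rule is in D2 2.b, Ethical Considerations. It reads, in part: "possible AN (low weight and significant weight shape concerns) at the 6-month or 2-year follow-up assessments, they will be offered a referral". The care offered is in person. The rule is not limited to one arm, and it names two of the three follow-up visits.

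The third visit is at 6 weeks. D1 says of it: "6 week assessments will ask participants to complete assessments of anxiety, depression, EDs" and some further items. This applies to both arms. The table in E2 marks the eating-disorder row at baseline, 6 weeks, 6 months and 2 years. It also marks a target-engagement row at baseline and 6 weeks, whose disorder-specific content is "avoidance; behavioral activation; restraint; weight/shape concerns".

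The abstract (A1) describes the trial population as "excluding anorexia nervosa, for which more intensive medical monitoring is warranted". D1 refers students with AN at screening and does not invite them to phase 2.

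**The concern.** The protocol treats AN as a condition its intervention should not manage alone. It refers for AN at screening, at 6 months and at 2 years, but not at 6 weeks, and it gives no reason for leaving that visit out. Weight/shape concerns, half of the AN criterion, are scheduled at 6 weeks for at least some participants.

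At stake is a prompt to a student who develops AN early, or whose AN the screen missed. The control arm is the more exposed, having no coach and no 6-week non-improvement rule. This is a participant-safety point only.

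**Working it through.** The plan states no figure to reproduce. The check sets the referral rules side by side and then computes the interval.

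**Routes to referral before 6 months**

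| Route | Source | Arm | AN-triggered? |
|---|---|---|---|
| Recommendation and resource list after baseline | D1 | Control | No |
| Email and text about screen responses | D1 | Both | No |
| Suicidality endorsed at any assessment, including 6 weeks | D2 2.b | Both | No |
| Adverse-event monitoring at every follow-up | E2 2.b, Reporting Procedures | Both | No |
| Coach judges the participant unsafe or in need of more intensive care | D2 2.b | Intervention | No |
| Coach judges that the program cannot handle comorbidity | D3 | Intervention | No |
| No symptom improvement by 6 weeks | D2 2.b | Intervention | No |

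The referral for people still in the clinical range covers both arms but uses the same two later visits, so it does not fill the gap. In the control arm, the only referral trigger stated for 6 weeks is suicidality.

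In the intervention arm, D3 says: "For individuals with eating disorders, weekly monitoring includes three questions based on the EDE-Q". The topics listed are binge eating, purging and weight/shape concerns. Body weight is not listed, though a coach might learn of low weight through messages or calls.

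**Can the criterion be scored at 6 weeks?** It needs two parts.

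- Weight/shape concerns: scheduled at 6 weeks, but as a disorder-specific mediator. The documents do not say that participants who entered for anxiety or depression are asked. The general eating-disorder assessment may cover it, but its items are not given.
- Low weight: no section says whether weight is collected at 6 weeks.

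**Interval** (visits counted from the baseline screen, D1)

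- 6 months in weeks: 6 × 30.4375 / 7 = 26.09.
- From 6 weeks to 6 months: 26.09 − 6 = 20.09, about 20 weeks. With 4-week months it is 24 − 6 = 18.
- If the 6-month survey is missed, the next AN trigger is at 2 years: 2 × 365.25 / 7 − 6 = 98.4 weeks after the 6-week visit.
- From 6 months to 2 years: 104 − 26 = 78 weeks, unaffected by the fix.

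**Result by case**

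- Both parts of the criterion collected at 6 weeks: about 20 weeks without an AN-triggered referral for an identifiable control case. In the intervention arm 20 weeks is an upper bound, since the coach routes and the non-improvement rule may act sooner.
- Weight not collected at 6 weeks: the rule causes no delay, because the criterion cannot be scored then. The surveys cannot detect a case until 6 months.

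No head count is computed, because the documents give no incidence of AN.

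**The case against.** The strongest reply is that the interval depends on an undocumented fact. If weight is first asked again at 6 months, a rule naming only 6 months and 2 years is exactly what one would write. The timing also matches the clinical-range referral, and the extra 6-week step for the intervention arm is explained as stepped care. Nothing in the protocol contradicts the rule. This stands, and it is why the point is an improvement and not a correction.

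Existing cover also counts. For controls, D1 states: "All students in the usual care condition will receive a recommendation to seek care and will be given a list of resources". After baseline, "participants will receive an email and text message with information about their screen responses". In the intervention arm, D3 adds: "If the coach feels the online program cannot adequately address comorbidity, participants are referred to appropriate campus/community resources". Adverse events are monitored at all follow-ups, and the principal investigators evaluate potential ones within 72 hours. A reader might infer that students with AN are left without care for 20 weeks. The documents do not support that: access is not withheld, and only a prompt tied to AN is missing.

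The comparison with suicidality is limited. It is a more acute risk, so its 6-week referral shows that such a prompt is feasible in both arms, not that AN calls for the same response.

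Finally, the fix adds a prompt to the usual-care arm at the first visit where Aim 1 uptake is measured. With so few cases expected, the effect on uptake should be negligible.

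**Conclusion.** The gap in the rule is real on the text: eating disorders are assessed in both arms at 6 weeks, and no AN-triggered referral exists then. It merits a minor, low-cost improvement to participant safety.

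Its size is conditional: about 20 weeks for an identifiable control case if both parts of the criterion are collected at 6 weeks, at most that in the intervention arm, and no delay caused by the rule if weight is not collected. The number affected is probably very small, because AN is screened out before phase 2, but it cannot be derived.

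Two stronger readings should be resisted. One is that the plan knowingly holds complete data on AN cases and ignores them. That would require weight to be collected at 6 weeks, which is not documented. The other is that the omission harms the trial's analysis. Nothing here bears on the estimand or power.

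**What to change.** - In D2 2.b, add the 6-week assessment to the two visits named in the possible-AN rule, for both arms.
- Make sure the 6-week survey asks every participant for weight (and height if not held from baseline) and for weight/shape concerns, whichever disorder they entered with.
- Deliver the referral as an automated Qualtrics message. D1 already plans automated feedback with an AN referral branch at screening.

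The cost is one protocol phrase, one automated message at an existing visit, and at most a few added survey items. A few extra control-arm prompts may follow. Aim 1 counts any session of online or in-person services (F3), so the effect on uptake should be negligible. The interval of about 78 weeks between 6 months and 2 years, with no scheduled assessment, remains.

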### **IRB of Record**

The use of a single IRB model is designed to enhance and streamline the process of IRB review and reduce inefficiencies without compromising ethical principles and protections within this multi-site clinical study. Each site signs an IRB Authorization Agreement to document the delegation of responsibilities of IRB review to WUSM and demonstrate WUSM's acceptance of these responsibilities.

## **2.c Subject Recruitment Plans and Consent Process**

Each participating school will provide us with a database of students from their registrar or academic information office. The database will contain a full population sample or random sample of undergraduate students. The database will include demographic information about students such as first name, email address, sex, race/ethnicity.

Students will be recruited via emails to their campus email address to participate in the screening assessment. Students will first receive a brief “pre-notification” email, which lets them know that an invitation to the study will be coming soon. Two to three days later, we will send the screening assessment recruitment email with a link to the online survey, and we will follow-up with reminder emails to non-responders. The emails will note that students can reply to decline participation (and any further reminders); they may also select this option on the consent form page of the screening survey.

Once students click on the survey link, students will be asked to review the consent information sheet, they will have all the time they need to review it. Full disclosure of the purpose of the study, the benefits and risks to individuals who participate, and the confidential nature of information obtained during the study will be explained to participants. Participants will be aware from the outset that they could be eligible for phase 2 of the study. Participants will be consented according to the policies and procedures of the WUSM IRB, the IRB of Record for the study. A trained study staff member will be available to students via phone to answer any questions they may have about their participation in the study.

We will follow-up with reminder emails to non-responders. The emails will note that students can reply to decline participation (and any further reminders); they may also select this option on the consent form page of the baseline survey.

For phase 2 eligible participants, following the personalized feedback , they will receive a brief statement of eligibility for and description of the study purpose and duration, activities involved, and assessment time points. Students will be asked to confirm their willingness to continue. If they agree students will be asked for their email address and phone numbers, and will be provided a link to the Phase 2 baseline survey. People who do not complete the baseline survey will be sent an email reminder to complete the survey.

---

Once students click on the survey link, students will be asked to review the informed consent before continuing with the baseline survey. Student will have all the time they need to review it. Full disclosure of the purpose of the study, the benefits and risks to individuals who participate, and the confidential nature of information obtained during the study will be explained to participants. Participants will be aware from the outset that they could be randomly assigned to a mobile health platform or referral to usual care. They will also be aware that their expected participation will last up to two years, including three additional follow-up assessments. Participants will be consented according to the policies and procedures of the WUSM IRB, the IRB of Record for the study. A trained study staff member will be available to students via phone to answer any questions they may have about their participation in the study.

## **2.d Randomization Method**

In phase 2, participants will be randomized after giving online consent, participants will be randomized via a code through Qualtrics into one of two conditions:

- 1) Intervention: receiving access to our mobile coached self-help program for 6 months.
- 2) Control: Receiving information on how to receive treatment at the student's counseling center on campus.

Participants will be made aware of the condition they were randomized into after completing the baseline survey.

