#### ***F4 Missing Outcome Data***

All analyses will be intent-to-treat analyses, using full-information maximum likelihood to handle missing data.

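### Students are randomized at consent but shown their arm only after the baseline survey, so under intention-to-treat those who abandon the survey can attenuate the effect or cost precision

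*Combined protocol and SAP*

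**What the plan says.** The order of steps is the same in two places. D1 states: "After giving online consent, participants will be randomized via a code through Qualtrics into one of two conditions". It continues: "Participants will then complete the baseline survey, which will assess treatment expectancy/credibility". D2 2.d gives the same timing ("participants will be randomized after giving online consent") and adds: "Participants will be made aware of the condition they were randomized into after completing the baseline survey". The means of reaching the condition also come afterwards. In D1: "After completing the baseline survey participants will receive an email and text message with information about their screen responses and either a link" to the program or, for controls, information on reaching clinical services.

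F4 states: "All analyses will be intent-to-treat analyses", with full-information maximum likelihood for missing data. No section defines the intention-to-treat set, says whether randomized students who did not finish the survey belong to it, or says whether they are followed.

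Three other places bear on the point:
- D1 offers follow-up to both groups, timed from the screen, with no condition that the baseline survey be complete.
- D1 collects counseling-center counts and registrar data in aggregate by assigned group.
- G1 describes an automatic SilverCloud sign-up email for students assigned to that program and does not say when it is sent.

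**The concern.** Until the survey is finished, a student in either arm has had the same experience: no disclosed arm and, on D1, no link or referral message. Any such student who contributes an outcome adds an expected difference of zero to the comparison.

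There are three possible routes: answering follow-up surveys; being counted in the aggregate counseling and registrar data, which need no survey response; or having missing uptake scored as no, which the plan neither adopts nor rules out. The aggregate data matter most, because likelihood methods cannot repair them and they cannot be re-subset once received. Uptake is the primary hypothesis (A2), so attenuation would reach the headline estimate even where power is ample.

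Abandoners also lack the measures that D1 places in the baseline survey, such as cognitive distortion, quality of life and motivation. Several of these are planned moderators. The documents give no reason for randomizing before the survey.

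**Working it through.** **Inputs.** 7,884 randomized (A1); 3,154 high-risk plus 3,154 clinical participants with complete follow-up, effect size .2, and power above 90% for primary outcomes (F1). The two figures of 3,154 are risk strata, not arms. Their total, 6,308, gives 3,154 per arm only under 1:1 allocation. Not stated, and assumed here: 1:1 allocation, two-sided 0.05, and abandonment *a* = 5 to 30%. The formulas ignore the college intercepts and repeated measures.

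**The plan's own figures.** 6,308 / 7,884 = 0.800, so a 20% loss is implied. The simulated power cannot be reproduced as a point value because its inputs are not given. Two readings of .2 bracket it:
- As a standardized mean difference: Φ(0.2·√(3,154/2) − 1.96) = Φ(5.98), above 99.9%.
- As a log odds ratio: 50% versus 45% gives ln(0.55/0.45) = 0.20. Power = Φ[(Δ − 1.96·SE0)/SE1], with SE0 = √(2p̄(1−p̄)/n) and SE1 = √((p1(1−p1)+p2(1−p2))/n). This is (0.05 − 1.96×0.012575)/0.012559 = 2.02, or 97.8%.

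Both agree with the stated figure of more than 90%.

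**Share of abandoners among those with outcomes.** If abandoners respond at rate *r* and completers at 0.8, the share is w = a·r / (a·r + 0.8(1−a)) and the expected effect is multiplied by (1 − w). With r = 0.8, w = a. With r = 0, w = 0 and the cost is sample size: n per arm = 3,154(1 − a).

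**Power at 50% versus 45%.**

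| Abandonment | Followed like completers: difference | Power | No follow-up: n per arm | Power |
|---|---|---|---|---|
| 0% | 5.00 points | 97.8% | 3,154 | 97.8% |
| 5% | 4.75 | 96.6% | 2,996 | 97.2% |
| 10% | 4.50 | 94.7% | 2,838 | 96.5% |
| 20% | 4.00 | 88.9% | 2,523 | 94.5% |
| 30% | 3.50 | 79.4% | 2,208 | 91.4% |

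Worked at 20%: followed, (0.04 − 1.96×0.012581)/0.012571 = 1.22, or 88.9%; not followed, (0.05 − 1.96×0.014060)/0.014042 = 1.60, or 94.5%. An unpooled standard error gives 79.5% in the last row. The no-follow-up columns put the loss on top of the implied 20%.

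**If .2 is a standardized mean difference.** Equal follow-up at 5/10/20/30% leaves 0.19/0.18/0.16/0.14. At 0.14, Φ(0.14·√1,577 − 1.96) = Φ(3.60), still above 99.9%.

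**Check on the likelihood method.** In a simulated two-time-point linear model (N = 7,884, true effect 0.20 in completers, 20% abandonment), the estimate was 0.20 when no abandoner responded, 0.19 when 20% did and 0.16 when 80% did. This is a linear stand-in for the planned logistic model.

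**Per student consented.** Randomizing after the survey with 7,884 consents leaves 3,154(1 − a) per arm at the full effect, so the last column is also the power of the revised order for the same number of consents. It is higher than the current order wherever abandoners are followed, and equal where none are.

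**The case against.** The strongest reply is that dilution is not automatic. A reader might infer that the effect shrinks by exactly the abandonment share. That holds only if abandoners answer follow-up as often as completers, and students who quit the first survey may well not. With no follow-up from them, maximum likelihood leaves the survey-based estimate nearly unchanged, the implied 20% loss may already absorb some of them, and the revised order gains nothing per consent. This stands for the survey outcomes. It does not reach the aggregate counseling and registrar data.

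Other parts of the reply also stand:
- Membership of the intention-to-treat set is an inference from the term, since the set is undefined.
- The reminder in D2 2.c ("People who do not complete the baseline survey will be sent an email reminder to complete the survey") might be read as showing abandonment after randomization. It appears before the consent step is described and may cover students who never opened the link or consented, so it does not establish a rate.
- It is tempting to say that abandoners have no baseline data. Anxiety, depression and eating-disorder status come from the screen (D1, E1 Table 3), so baseline caseness and symptoms exist.
- It is tempting to say that they can never reach the program. The G1 sign-up email leaves that open.
- 50% versus 45% is the less favourable of the two readings of .2 used here.

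**Conclusion.** The order of steps is a real and avoidable weakness of modest, unknown size. If the arm is concealed until the survey ends, as D1 and 2.d say, abandonment before disclosure cannot depend on the arm. A reader might infer bias favouring one arm; the documents do not support that. What follows is attenuation where abandoners contribute outcomes and lost precision where they do not.

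On the log-odds reading, power drops below 90% only at about 20% abandonment with equal follow-up; without follow-up it stays above 90% up to 30%. On the standardized-mean reading, power is not threatened, though the estimate can still be attenuated. All of this rests on an assumed abandonment range, 1:1 allocation, two-sided 0.05 and a 50% control rate. The conclusion that there is no selection by arm depends on the G1 email not going out before the survey is finished.

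**What to change.** Move the Qualtrics randomization step to submission of the pre-disclosure baseline measures, immediately before the arm is shown and before the credibility questionnaire that D1 places after disclosure. Change the matching sentences in D1 and 2.d, and state in F4 that the intention-to-treat set is everyone so randomized. This moves one survey block. It needs 7,884/(1 − a) consents for the same randomized number: 8,299, 8,760, 9,855 or 11,263 at 5, 10, 20 or 30%.

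If enrolment has begun, prespecify the analysis set as randomized students who completed the pre-disclosure measures. Use the same set as the denominator in the requests to counseling centers and registrars, settled before those data are obtained. Report abandonment by arm. The cut must not be later, because drop-out after disclosure could differ by arm.

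In either case, reconcile D1, 2.d and G1 on when the automatic sign-up email is sent. If it can arrive before the survey is finished, concealment may already have failed in one arm and the restricted set is no longer safe.
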